#### **4.2.2 Variables of Interest (or Endpoint) to be Obtained for Each Subject that is Required to Address the Scientific Question**

The co-primary endpoints to be obtained for each subject in this study to address the scientific question are [tissue eosinophil responders](#) (as defined in Table 2) at Week 24 and change in DSQ from baseline to Weeks 23–24 as measured by the patient reported outcome (PRO) questionnaire.

#### **4.2.3 Treatment**

AK002 or placebo administered to subjects on Days 1, 29, 57, 85, 113, and 141.

#### **4.2.4 Intercurrent Events**

The events below are considered intercurrent events (ICE) confounding with the efficacy outcomes.

- Premature discontinuation from the study
- Use of prohibited/rescue medication
- Any therapeutic EGD (defined as dilatation or other intervention for a narrowing or stricture of the esophagus) at any point during the study through Week 24.

Further clarification and handling of ICE including prohibited/rescue medications is detailed in [Appendix 2](#).

#### **4.2.5 Strategy for Handling Intercurrent Events**

Per the study protocol, if a prohibited medication is started during the course of the study, the subject will be withdrawn from study treatment and followed for the 12-week follow-up period. In addition, the follow-up EGD may not be performed. Thus, for analysis of the trial product estimand, tissue eosinophil values and DSQ scores will be counted as non-responders for binary variables and set to missing for continuous outcomes from the point when an ICE occurs. An appropriate method for handling missing data through statistical modeling (e.g., multiple imputation [MI]) will be used (Sections [5.4.1](#), [5.4.2](#), and [6.11](#)). The estimand will provide an answer to the question that is crucial to individual subjects:

“If I take this study drug as part of my treatment regimen, without adding any further medications or the use of therapeutic endoscopic interventions that may impact the underlying disease or exit the study prematurely, what improvements in histology and PRO symptoms might be anticipated after 24 weeks?”

#### 4.2.6 Summary Measure of Estimand

- Percent (and 95% confidence interval [CI]) of subjects having tissue eosinophil response at Week 24 in the AK002 and placebo treatment groups and the absolute difference (and 95% CI) in the percent response between treatments.
- Least squares mean (LSM) (and standard error [SE]) of change from baseline to the average of Weeks 23–24 DSQ and the between treatment difference in the AK002 and placebo treatment groups LSM.

### 5. Statistical Methods

#### 5.1 General Methodology

All statistical analyses will be conducted using SAS v 9.4 or later version on the Microsoft Windows Operating System.

All CRF data (raw data) will be converted into SDTM (Study Data Tabulation Model) datasets, which will be used to create ADaM (Analysis Data Model) data sets. The creation of the SDTM and ADaM data sets will follow the CDISC (Clinical Data Interchange Standards Consortium) standards and the FDA Study Data Technical Conformance Guide. All analysis tables and listings will be created from the ADaM data sets.

Continuous data will be summarized using “n” (number of subjects with non-missing observations), mean, median, SD, minimum value, and maximum value. Categorical data will be summarized using the frequency count and percentage (n, %) of subjects in each category. Number of subjects with non-missing values or number of subjects with missing values (e.g., Not Done) will be presented, where appropriate. Subjects with missing values will not contribute to the denominator for percentage calculations, unless specified otherwise. Counts of 0 in any category will be presented without percentage. All summaries will be presented for individual treatment groups. In addition, for summary of disposition and subject baseline characteristics, the presentation will include each treatment group, the placebo, and the overall study population.

The precision rules for the presentation of summary statistics will be:

- Sample size (n, N) and number of missing responses (if displayed): Integer
- Mean, confidence interval, and median: Same number of decimal places as reported/collected
- Standard deviation: Same number of decimal places as reported/collected
- Percentiles, minimum, maximum: Same number of decimal places as reported/collected

- Odds Ratio: 2 decimal places
- Percentage: 1 decimal place generally, or 2 decimal places for <0.1%, or no decimal places for 0% and  $\geq 100\%$
- P-value: 4 decimal places
- WBC: 2 decimal places as  $0.01 \times 10^9/L$
- Height/Weight/BMI: 1 decimal place

The data summaries will be accompanied by individual subject data listings. All data available from questionnaires, eCRF, and external transfer (labs) will be listed and will include relevant subject information, e.g., treatment group and study day. The listings will be sorted in the order of treatment group, subject ID, assessment name, and date/time.

Dates will be presented in the ISO-8601 format YYYY-MM-DD. Times will be displayed in 24-hour clock format. Numbering for tables, figures and listings will follow ICH E3 Guideline (ICH, 1996).

Alternative methods of analysis of the data may be considered prior to database lock should some of the assumptions underlying the proposed analyses not be met. Reason for departure from the planned methods will be documented as an amendment to the SAP or in the CSR.

## 5.2 Visit Window and Unscheduled Assessments

Data collected for study assessments provide information on the status of the subject at a given time point. These may provide biased results if the assessment is performed early or late. Therefore, assessments will be slotted into analysis windows to allow summaries to be performed for subjects with similar study drug exposure. The analysis window is constructed by the medians of 2 target study days of the adjacent planned visits.

**Table 3** Analysis Window Rules for **CCI**

Visit Description	Window
Baseline	On or Prior to Day 1 Predose
Day 1	Predose on infusion Day 1
Day 29	Day 1 Postdose to Day 42
Day 57	Day 43 to Day 70
Day 85	Day 71 to Day 98
Day 113	Day 99 to Day 126
Day 141	Day 127 to Day 154
Day 169	Day 155 to Day 186
Day 197	Day 187 to End of Study

**Table 4** Analysis Window Rules for Vital Sign and Laboratory Tests

Visit Description	Window
Baseline	On or Prior to Day 1 Predose
Day 1	Day 1 Postdose
Day 15	Day 2 to Day 22
Day 29	Day 23 to Day 42
Day 57	Day 43 to Day 70
Day 85	Day 71 to Day 98
Day 113	Day 99 to Day 126
Day 141	Day 127 to Day 154
Day 169	Day 155 to 186
Day 197	Day 187 to End of Study

**Table 5 Analysis Window Rules for PK Concentration and ADA**

Visit Description	Window
Baseline	On or Prior to Day 1 Predose
Day 8	Day 1 Postdose to Day 11
Day 15	Day 12 to Day 22
Day 29	Day 23 to Day 42
Day 57	Day 43 to Day 70
Day 85	Day 71 to Day 98
Day 113	Day 99 to Day 126
Day 141	Day 127 to Day 154
Day 169	Day 155 to Day 172
Day 176	Day 173 to Day 186
Day 197	Day 187 to Day 210

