19.12 Appendix 12: Open-Label Extended Dosing Period (Optional)

19.12.1 Summary of the Open-Label Extended Dosing Period

Subjects who complete the double-blind, placebo-controlled treatment period (including the Day 169 study visit) and meet the open-label extended dosing eligibility criteria will be given the option to receive 6 doses of AK002 through the Open-Label Extended Dosing Period (OLE).

On Day 176 (± 3 days), eligible subjects participating in the OLE period will begin following the OLE Schedule of Events (Table 5) and will no longer follow the Schedule of Events in Table 1.

The Extended Dosing Period is summarized as follows:

- The Investigator will evaluate whether the subject is eligible for OLE. If eligible, the subject will be given the option to participate in the OLE period and receive 6 doses of open-label AK002.
- On Day 176 (± 3 days), eligible subjects who choose to participate in the OLE period will begin following the OLE Schedule of Events (Table 5).
- 12–24 hours prior to the first open-label AK002 infusion only, subjects will self-administer oral prednisone premedication (40 mg if body weight is < 40 kg, 60 mg if body weight is ≥ 40 kg and < 60 kg, or 80 mg if body weight is ≥ 60 kg).
- OLE subjects will receive 6 doses of open-label AK002 administered on Days 176 (± 3), 204 (± 3), 232 (± 3), 260 (± 3), 288 (± 3), and 316 (± 3). The first open-label AK002 infusion will be given at a dose of 1 mg/kg. For subsequent open-label AK002 infusions on Days 204 (± 3), 232 (± 3), 260 (± 3), 288 (± 3), and 316 (± 3), each infusion may be given at a dose of either 1 mg/kg or 3 mg/kg at the discretion of the Investigator.
- Subjects will remain at the site for at least 1 hour of observation after each dose. In the event of an IRR, the subject may require prolonged observation (> 1 hour or until the symptoms resolve), as per Investigator discretion.
- Subjects will be followed for approximately 8 weeks after the last dose. Follow-up visits will occur on Day 344 (± 7) and Day 372 (± 7).
- If absolute lymphocyte and/or eosinophil counts have not recovered by the OLE Day 372 visit, subjects will return approximately every 28 days for extended follow-up until counts have recovered.

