PK: Pharmacokinetics

Table 5 Notes

- 1) Refer to assessment footnote for specific timing (e.g., predose, during infusion, postdose).
- 2) The Investigator will evaluate whether the subject is eligible for the OLE period per Section 19.12.3. On Day 176 (± 3 days), eligible subjects that choose to participate in the OLE period will begin following the OLE Schedule of Events and will receive the first open-label AK002 infusion.
- 3) Subjects should complete the DSQ daily after the last meal of the day. If Question 1 is answered “No,” the subject should answer the Solid Food Question ([Appendix 2](#)) after the DSQ is completed and submitted. The site is responsible for monitoring compliance and discussing compliance during study visits.
- 4) **CCI** should be the first assessment completed by the subject at the beginning of the study visit prior to other assessments.
- 5) Per Inclusion Criterion #7, subjects should maintain the baseline diet consistently throughout the study. Diet compliance will be discussed during study visits and any variance will be documented.
- 6) Weight will be measured predose on Days 176, 204, 232, 260, 288, and 316, and Days 344 and 372 (or ET).
- 7) Vital signs will be measured at all OLE visits. On dosing days (Days 176, 204, 232, 260, 288, and 316), vital signs will be measured predose, 15 minutes (± 5 minutes) after infusion start, immediately postdose (within 5 minutes after infusion end), and 1 hour (± 5 minutes) postdose. Subject should be at rest for ≥ 5 minutes before vital signs (systolic and diastolic blood pressure, pulse, body temperature, and respiratory rate) are measured.
- 8) Please see the Central Laboratory Manual for collection, processing, and shipment instructions. Samples should be shipped on the same day as collection.
- 9) Blood for total serum IgE will be obtained predose on Day 316 and again on Day 372 (or ET).
- 10) Blood for CBC with differential will be obtained at all OLE period study visits. On Days 176, 204, 232, 260, 288, and 316, blood will be drawn twice (predose and 1-hour postdose).
- 11) Blood for chemistry will be obtained at all OLE period study visits. On Days 176, 204, 232, 260, 288, and 316, blood for chemistry will be drawn predose.
- 12) Blood for PK will be obtained at all OLE period study visits. On Days 176, 204, 232, 260, 288, and 316, blood for PK will be drawn predose.

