- 22) An EGD with biopsy collection will be performed on Day 344 (\pm 3 days). EGD biopsies will be collected, processed, and shipped in accordance with [Appendix 9](#), the central laboratory manual, and the histology manual.
- 23) During the Day 344 EGD, severity will be evaluated using the EoE Reference Score for Endoscopic Abnormalities per the AK002-014 Histology Manual.
- 24) All AE, including AESI and SAE, will be captured through the entire OLE period until Day 372 (or ET). Adverse events will be assessed and recorded in the CRF of the AK002-014 OLE period database beginning from the start of the first open-label infusion during the Day 176 visit.
- 25) The ET visit should be conducted 28 (\pm 3) days after the last dose of open-label AK002 or prior to this, if necessary, to ensure compliance with the visit. If ET occurs after the Day 204 study visit and before the Day 344 study visit, then an EGD with biopsy collection must be done 28 (\pm 3) days after the last dose of open-label AK002. If a subject discontinues the study >28 days after the last dose of study drug, the ET visit should be conducted as soon as possible.
- 26) If absolute lymphocyte and/or eosinophil counts do not recover (to normal range or baseline levels) by Day 372 (or ET), extended follow-up visits are required every 28 days (\pm 3 days) thereafter to monitor blood counts until they recover. Extended follow-up visits consist of blood collection for CBC with differential and collection of AESI and SAE.
- 27) Sites should strive to conduct visits within a \pm 3 day window, but visits conducted within \pm 7 days are acceptable and are not considered deviations. Visits conducted \pm 4-7 days from the target visit date should be minimized as much as possible. Any visit conducted outside of the \pm 3 day window should receive prior written approval from Allakos.

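### Read as written, the SAP's Day 197 windows count Day 204 laboratory and vital-sign values taken after open-label AK002, including those of former placebo subjects, as Day 197 of the randomised arm

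*SAP*

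**What the plan says.** **Windows.** SAP 5.2 places each assessment in a visit by study day. The Day 197 row is "Day 187 to End of Study" in Table 3 (a questionnaire), Table 4 (vital signs and laboratory tests) and Table 6 (blood histamine and urinalysis). In Table 5 (PK and ADA) it is "Day 187 to Day 210". Table 5 alone also has a Day 176 row, "Day 173 to Day 186". No row refers to the first open-label infusion or depends on whether the subject entered the open-label period.

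**Open-label schedule.** Protocol 19.12.1 starts open-label dosing on Day 176 for every entrant: "The first open-label AK002 infusion will be given at a dose of 1 mg/kg". The schedules of events state that the Day 197 visit does not apply to these subjects. Their next visit is Day 204, with vital signs, blood count and chemistry. For PK, protocol Table 5 note 12 says "Blood for PK will be obtained at all OLE period study visits". ADA on Day 204 is drawn only for a suspected immunogenicity-related adverse event (note 13).

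**Use in the tables.** SAP 6.15.2 applies the windows to the laboratory summaries, and SAP 6.15.3 applies them to vital signs. SAP 5.1 presents summaries by treatment group. SAP 6.14 summarises PK by nominal time point, without saying whether that means the protocol visit or the analysis window.

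**The concern.** SAP 5.2 gives the purpose of windowing as grouping subjects whose exposure to study drug is alike. For Day 197 the rule does the opposite. Subjects who stayed off open-label drug are at Day 197, eight weeks after their last blinded infusion (141 + 56 = 197). Open-label entrants enter the same row four weeks after a new AK002 infusion.

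The placebo arm matters most. Protocol 2.3 and 11.2.8 describe sustained eosinophil depletion as an expected effect of AK002. A placebo Day 197 row that mixes in former placebo subjects after their first AK002 dose could show that depletion in the hematology change and shift tables. The placebo comparison at that visit would be blunted or misleading. In the two AK002 arms the row would no longer describe what happens eight weeks after treatment stops.

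**Working it through.** **1. Reproduce the plan's window.** SAP 5.2 says "The analysis window is constructed by the medians of 2 target study days of the adjacent planned visits". So boundary = (earlier target + later target) / 2, with an exact midpoint day going to the later visit, as in most table rows.
- Days 169 and 176: 345 / 2 = 172.5, so Day 169 ends on Day 172. Matches Table 5.
- Days 176 and 197: 373 / 2 = 186.5, so Day 197 starts on Day 187. Matches.
- Days 197 and 225: 422 / 2 = 211, so Day 197 ends on Day 210. Matches, taking the first extended follow-up as 197 + 28 = 225.

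**2. Place the Day 204 visit (176 + 28 = 204).** Protocol Table 5 targets ±3 days, but note 27 says visits within ±"7 days are acceptable and are not considered deviations".
- At ±3 (Days 201–207): all 7 days fall in the Day 197 row of every table.
- At ±7 (Days 197–211): 14 of 15 days fall in the Table 5 row (only Day 211 escapes) and all 15 in Tables 3, 4 and 6.

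If End of Study means Day 372 for these subjects, the visits on Days 232, 260, 288, 316, 344 and 372 also fall in the Day 197 row of Tables 3, 4 and 6.

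**3. Exposure at that point.** The first open-label infusion falls on Days 173–179 at ±3 and Days 169–183 at ±7. Since 183 < 187, every open-label visit sample in a Day 197 window follows open-label AK002, by 204 − 176 = 28 days on target.

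**4. Competing values.** Open-label entrants have no true Day 197 sample. Of their later visits, Day 204 is nearest to target (7 days away; the next, Day 232, is 35 days away).

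**5. The Day 169 row.** In Tables 3, 4 and 6 it runs to Day 186. The midpoint of 169 and 197 is 183, which would end it on Day 182; Day 186 is the Day 176/197 bound. All possible first-infusion days (169–183) lie inside it, so the 1-hour postdose blood count on Day 176 is inside it too. The true Day 169 value is nearer its target, so this is a lesser problem, but the row still spans the first open-label dose.

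**6. Scale.** The documents give no expected open-label uptake for this trial. Placebo subjects remaining: 100 × (1 − 0.14) = 86.

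| Assumed uptake | Former placebo subjects in the placebo Day 197 row | True Day 197 placebo subjects |
|---|---|---|
| 0% | 0 | 86 |
| 50% | 43 | 43 |
| 90% | 77 | 9 |
| 100% | 86 | 0 |

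**7. After a cut-off.** If each window closes at the subject's first open-label infusion, no Day 204 value can fall in Day 197. Adding Day 204 as a planned visit works less well: (197 + 204) / 2 = 200.5 ends Day 197 on Day 200. That excludes Days 201–207 but, at ±7, still admits Days 197–200.

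**The case against.** The best reply is that these are double-blind windows and open-label data were never meant to enter them. SAP 3.2 leaves the open-label period out of its schedule, and Table 1 labels Day 197 as end of study. An entrant completes the double-blind portion at Day 169. Protocol 15.1 assigns open-label data to additional analyses. A separate open-label database exists. The Day 210 limit in Table 5 fits a schedule without Day 204.

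This supports the intent but does not supply the rule. The database split is written for adverse events, adverse events of special interest and concomitant medications, not for laboratory, PK or vital-sign data. Protocol 15.1 gives no rule for assigning samples. Day 176 is solely an open-label visit, so its row in Table 5 shows that samples from an open-label visit do enter the windows. If End of Study meant the Day 197 visit, entrants would have no such visit to close the window. Even its latest accepted day, 197 + 7 = 204, would admit a Day 204 sample taken on target.

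Other parts of the reply stand, and they rule out stronger readings that a reader might infer:
- **That ADA results are corrupted.** Day 204 ADA is event-driven, and SAP 6.15.6 summarises ADA as positive at any time after dosing and at end of study, not by Table 5 rows.
- **That PK is certainly affected.** If nominal time means the protocol visit, Day 204 PK is not labelled Day 197.
- **That the Day 176 row is itself contaminated and should go.** Scheduled PK and ADA on Day 176 are predose. Blinded-period ADA is not drawn on Day 169, so for entrants this is the only scheduled ADA sample after Day 141 and before open-label drug.
- **That the nearest-value rule clearly selects Day 204.** It is written for unscheduled and early-termination values. Without it, though, the plan has no stated rule for choosing among several scheduled values in one window.
- **That "All data available from questionnaires, eCRF, and external transfer (labs) will be listed" proves contamination.** That sentence concerns listings, which keep the visit as the site reported it.

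**Conclusion.** The point holds on the written rule and is firmest for Table 4, because the SAP expressly uses those windows for the laboratory and vital-sign summaries. Tables 3 and 6 share the open-ended wording. In Table 6 the exposure is narrower, since open-label urinalysis is scheduled only predose on Day 176 and on Day 372, and otherwise as needed. Table 5 has the same problem for PK only if nominal time point means the analysis window.

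The size depends on uptake: about 43, 77 or 86 of some 86 placebo subjects at 50%, 90% or 100%. A reader might take the more than 90% continuation after the Phase 2 study and conclude that 90 of 100 placebo subjects are affected. The documents do not support that figure. The continuation rate comes from a trial in eosinophilic gastritis and duodenitis, and 90 of 100 ignores the plan's own 14% dropout.

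The consequence is limited. The co-primary endpoints (Week 24 biopsy, Weeks 23–24 DSQ) do not use these windows, protocol 15.1 plans no formal inference on safety, and the provisional lock covers data through Day 169. What is at risk is a descriptive post-treatment row. It is a minor point, but the stated rule gives a wrong result and is cheap to correct.

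**What to change.** Amend SAP 5.2 before unblinding:
- For subjects entering the open-label period, close all double-blind windows, including the Day 169 rows that run to Day 186, at the start of the first open-label infusion. Later values are summarised under their own open-label visits.
- Limit the Day 197 row in Tables 3 to 6 to subjects who did not enter the open-label period, and label it so.
- Keep the Day 176 row of Table 5, restricted to the predose sample.
- State in SAP 6.14 whether nominal time point means protocol visit or analysis window, and define End of Study in the window tables.

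No endpoint, alpha level or sample size changes. The cost is a smaller Day 197 row: on the assumptions above, 43, 9 or 0 placebo subjects at 50%, 90% or 100% uptake. Those who remain were ineligible for open-label dosing or declined it, so the row should be read as describing them and not the whole randomised arm. If the programmers already intend this cut-off, the amendment only documents it.

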**Table 6 Analysis Window Rules for Blood Histamine and Urinalysis**

Visit Description	Window
Baseline	On or Prior to Day 1 Predose
Day 1	Predose on Day 1
Day 15	Day 1 Postdose to Day 18
Day 29	Day 21 to Day 42
Day 57	Day 43 to Day 70
Day 85	Day 71 to Day 98
Day 113	Day 99 to Day 126
Day 141	Day 127 to Day 154
Day 169	Day 155 to Day 186
Day 197	Day 187 to End of Study

In the event of multiple values from unscheduled or early termination assessments within a single analysis window, the value closest to the scheduled visit target study day will be used for analyses. If 2 values tie as closest to the time point (for example, a value is before and the other value is after the time point), then the later value will be selected. Data collected at all visits will be included in the data listings with visit presented as reported by the site.

### 5.3 Adjustment for Covariates

Efficacy analyses will be adjusted for baseline values and randomization stratum using analysis of covariance (ANCOVA), mixed model for repeated measures (MMRM), or Cochran-Mantel-Haenszel (CMH) tests, where applicable.

